### 6.4. Patient Completion of the Study

Patients are expected to remain on study treatment until at least completion of Cycle 6. Patients who have not demonstrated disease progression or unacceptable toxicity may continue to receive study treatment beyond 6 cycles.

Patients are considered to have completed the study treatment period when they finish the Safety Follow-up Visit 30 days (± 7 days) after their last dose of study treatment, unless they are experiencing ongoing serious adverse events (SAEs) or treatment-related AEs. For patients being followed for ongoing SAEs or treatment-related AEs, follow-up visits will continue at least Q4W until resolution to baseline or stabilization of these events, unless the patient starts another anti-cancer treatment. Follow-up for ongoing SAEs or treatment-related AEs after the Safety Follow-up Visit will stop if a patient begins another anti-cancer therapy.

After the Safety Follow-up Visit, patients will enter long-term follow-up for disease progression (Section 7.6) and survival follow-up (Section 7.7).

All patients, including those who discontinue study treatment early, will be followed for response until disease progression or initiation of new anti-cancer therapy, whichever happens first, and followed for survival until death or 3 years after the date of enrollment of the last patient, whichever happens first. For patients who come off study treatment to receive a bone marrow transplant, follow-up for disease progression and collection of SOC bone marrow biopsy/aspirate results will continue until documented disease progression occurs. For any patient who dies during this period, the cause of death must be reported to the Sponsor. All patients must also be followed through completion of all study treatment.

Patients are considered to have completed study participation altogether when they are no longer followed for disease progression or survival (refer to Section 8 for additional details about study discontinuation).

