# 7.9. Efficacy Assessments

Clinical response will be assessed using the guidelines in Appendix B, which are based primarily on 2017 ELN recommendations (Döhner 2017) and IWG criteria (Cheson 2003 and Cheson 2006), as described in Section 10.

Response assessments will be done in conjunction with bone marrow assessments, according to the Schedule of Assessments in Section 7.1. Accompanying laboratory results  $\pm$  2 weeks from the protocol-specified bone marrow efficacy assessment can be used to support an efficacy assessment of CR for both AML and MDS. These supporting lab results will be entered into the clinical database to capture response. Response assessments are scheduled on Day 1 of every other treatment through Cycle 7 and then every third cycle during study treatment for all cohorts, with an additional response assessment on Day 1 of Cycle 2 for the R/R Cohorts only.

If a patient achieves a CR (including morphologic CR, CRMRD-, cCR, and mCR), subsequent bone marrow biopsies are still required to be performed as per the Schedule of Assessments (Section 7.1).

Response assessment will be obtained at the EOT visit (within 7 days of the decision to end treatment), unless a prior response assessment has been performed within the last 7 days or progressive disease has been documented. If the patient discontinues treatment without documented progressive disease, a response assessment should be done at the Safety Follow-up visit if one has not been done within the prior 4 weeks. Response assessments should continue during long-term follow-up approximately every 8 weeks until progressive disease is documented or the patient starts a new anti-cancer therapy.

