#### 8. STUDY DISCONTINUATION

# 8.1. Discontinuation of Study Drug Treatment

Patients (or a legally acceptable representative) may decline to continue receiving study drug at any time during the study, but will continue follow-up study visits unless they withdraw completely from the study (Section 8.2). The patient's health and welfare is the primary consideration in any determination to discontinue study drug treatment. Patients who discontinue study drug during the treatment period are to return for an EOT visit for evaluation of safety within 7 days of the decision to end magrolimab treatment if no evaluation was done within 7 days of the decision. In addition, patients are to return for a Safety Follow-up Visit 30 days (± 7 days) after their last dose of study drug. All patients who discontinue study drug treatment will participate in long-term follow-up for disease response until documented disease progression or initiation of new anti-cancer therapy, unless the patient withdraws consent for such follow-up and withdraws completely from the study (Section 8.2). For patients who come off study treatment to receive a bone marrow transplant, follow-up for disease progression and collection of SOC bone marrow biopsy/aspirate results will continue until documented disease progression occurs. All patients will be followed for survival until the end of the study. The assessments to be performed at each of the post-treatment visits are listed in the Schedule of Assessments, Section 7.1.

Reasons for discontinuation of study drug treatment may include, but are not limited to, the following:

- Disease progression with confirmation in subsequent assessment at least 4 weeks apart (i.e., disease worsening compared to the previous assessment)
- Unacceptable toxicity
- Clinically significant change in the patient's status that precludes further treatment (e.g., pregnancy or other AE)
- Patient request, with or without a stated reason
- Bone marrow transplant
- Investigator or treating physician decision in the absence of any of the above.

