#### 10. MEASUREMENT OF EFFECT

Assessment of response will be conducted by the Investigator using the criteria in Appendix B, which are based primarily on the 2017 ELN recommendations for AML (Döhner 2017) and the 2003 IWG criteria (Cheson 2003) for AML patients. Response classifications include: complete remission (CR) rate, morphologic CR, complete remission without minimal residual disease (CRMRD-), cytogenetic complete remission (cCR), molecular complete remission (mCR), complete remission with incomplete hematologic recovery (CRi), complete remission with partial hematologic recovery (CRh), marrow complete remission (CR), morphologic leukemia-free state (MLFS), PR, and stable disease (SD).

In addition, hematologic improvement (HI) will be assessed by 2006 IWG criteria (Cheson 2006) to compare with disease response assessed by 2017 ELN criteria (Döhner 2017) and 2003 IWG criteria (Cheson 2003).

Response will be assessed in MDS patients using the criteria in Appendix B Table 14-4, which are based on the 2006 IWG criteria (Cheson 2006) with the added caveat that the impact of anemia must be deemed disease-related and not due to study treatment.

Response assessments will be performed at the time points specified in the Schedule of Assessments in Section 7.1 and as described in Section 7.9.

The following summary measures for endpoints will be evaluated:

**Objective Response Rate for Patients with AML**: The ORR is the proportion of patients who reach CR (including morphologic CR, CRMRD-, cCR, and mCR), CRi, CRh, PR, or MLFS while on study.

**CR Rate for Patients with AML**: The CR rate is the proportion of patients who achieved CR, as defined by the Investigator based on ELN AML recommendations (Döhner 2017; Appendix B).

**CR Rate for Patients with MDS**: The CR rate is the proportion of MDS patients who reach morphologic CR while on study per IWG 2006 criteria (Cheson 2006).

**Duration of Complete Remission (DCR) for AML**: The DCR is measured from the time measurement criteria are first met for CR (including morphologic CR,  $CR_{MRD}$ -, cCR, and mCR) until the first date that recurrent disease or death with evidence of no disease recurrence is objectively documented. Those who are not observed to have recurrent disease or die with evidence of no recurrence during the trial active period will be censored at their last response assessment date with evidence of no progression/recurrence.

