### 11.8.1. Efficacy Analyses

## 11.8.1.1. Primary Efficacy Endpoint: CR Rate

The primary efficacy endpoint for both AML and MDS is CR rate as assessed by Investigators. The analysis of CR rate will be conducted on all enrolled patients who receive at least 1 dose of the investigational drug magrolimab. In addition, an evaluable patient efficacy analysis will be performed on all enrolled patients who receive at least 1 dose of magrolimab and have at least 1 disease response assessment or who died before the first post-treatment disease response assessment. The point estimate of the CR rate and the corresponding 2-sided 95% confidence interval will be generated.

For the primary analysis of TN/U higher-risk MDS patients, the percentage of patients achieving a CR will be estimated based on all TN/U higher-risk MDS patients who received at least 1 dose of magrolimab, with exact 95% CI using the Clopper and Pearson method. Formal hypothesis testing will be performed to test the statistical hypothesis of:

 $H_0$ : CR rate = 23.5%; vs.

 $H_1$ : CR rate ≠ 23.5%.

The Chi-square test will be performed at 2-sided 0.05 significance level.

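### The registrational CR rate has no cut-off at transplant or new therapy, so a first CR reached after a bone marrow transplant can be counted for magrolimab + azacitidine

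*Protocol*

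**What the plan says.** **The endpoint.** Section 10 gives the MDS CR rate as "The CR rate is the proportion of MDS patients who reach morphologic CR while on study per IWG 2006 criteria". The AML objective response rate is likewise the share reaching CR, "CRi, CRh, PR, or MLFS while on study". The AML CR rate in the same section has no time window at all. Section 11.8.1.1 keeps every treated patient in the primary analysis ("the percentage of patients achieving a CR will be estimated based on all TN/U higher-risk MDS patients who received at least 1 dose of magrolimab"), tests the rate against 23.5%, and adds no cut-off.

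**When a patient is on study.** Section 8.1 lists "bone marrow transplant" as a reason to stop study drug. It is not among the reasons for leaving the study in Section 8.2. Section 6.4 says: "Patients are considered to have completed study participation altogether when they are no longer followed for disease progression or survival".

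**When response follow-up stops.** Section 6.4 says that all patients "will be followed for response until disease progression or initiation of new anti-cancer therapy, whichever happens first". Section 7.9 agrees: "Response assessments should continue during long-term follow-up approximately every 8 weeks until progressive disease is documented or the patient starts a new anti-cancer therapy". Section 7.3.8 has the same rule.

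**The transplant exception.** For patients who leave treatment for a transplant, Section 6.4 continues: "follow-up for disease progression and collection of SOC bone marrow biopsy/aspirate results will continue until documented disease progression occurs". Sections 7.6 and 8.1 and footnote a of Table 7-5 repeat this.

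**The concern.** Being on study lasts much longer than being on treatment. A TN/U higher-risk MDS patient could go to transplant in marrow CR, PR or stable disease. Afterwards that patient could have at most 5% marrow blasts and recovered counts from the donor graft. Read literally, this meets the Section 10 definition, and no sentence in the protocol excludes it.

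The MDS Registrational Cohort is a single arm intended to support a potential licence application, and its CR rate is compared with a fixed 23.5%. There is no control arm in which post-transplant remissions would also occur. Any CR owed to conditioning and a graft would therefore read as an effect of the study drugs.

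**Working it through.** **1. The plan's own figure.** Inputs from Sections 11.4 and 11.8.1.1: n = 92, null p0 = 0.235, alternative p1 = 0.365, chi-square test at 2-sided 0.05, stated power 80%.

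Power = Φ{[(p1 − p0)√n − 1.96√(p0(1 − p0))] / √(p1(1 − p1))}
= Φ{[0.13 × 9.592 − 1.96 × 0.4240] / 0.4814}
= Φ(0.864) = 80.6%.

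The stated 80% reproduces. The sample size is not in question.

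**2. The rejection boundary.** The chi-square statistic is n(x/n − p0)² / [p0(1 − p0)], compared with 3.84.
- x = 29: 3.29, not rejected.
- x = 30: 4.25, rejected.

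At least 30 of 92 CRs (32.6%) are needed. The null expectation is 92 × 0.235 = 21.6, so about 8 extra CRs reach the boundary.

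**3. The passages side by side.**

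| Question | Protocol text | Result |
|---|---|---|
| Does transplant end study participation? | 6.4, 8.1, 8.2 | No; it ends study drug only |
| Does new anti-cancer therapy end response follow-up? | 6.4, 7.3.8, 7.9 | Yes |
| Is transplant new anti-cancer therapy? | Not stated | Open |
| Does follow-up go on after transplant? | 6.4, 7.6, 8.1, Table 7-5 footnote a | Yes, to progression |
| Does the CR definition exclude a CR first met after transplant? | 10, 11.8.1.1 | No |

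In Table 7-5, footnote a is attached to the long-term follow-up column. That column schedules both a marrow and a response assessment every 8 weeks.

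**4. Sensitivity of the test.** Suppose the true drug CR rate equals the null and post-transplant CRs add a few points to the observed rate. The exact binomial P(X ≥ 30), n = 92, is:

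| Added points | Expected extra CRs | Rate | P(X ≥ 30) |
|---|---|---|---|
| 0 | 0 | 23.5% | 2.9% |
| +2 | 1.8 | 25.5% | 7.7% |
| +4 | 3.7 | 27.5% | 16.3% |
| +6 | 5.5 | 29.5% | 29.1% |

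**5. How many extra CRs are plausible.** The protocol gives no transplant rate, so these inputs are assumptions: 10–30% of patients transplanted, 30–50% of those not in CR at transplant, 50–70% of those in CR afterwards.
- Low: 92 × 0.10 × 0.30 × 0.50 = 1.4 CRs (1.5 points).
- High: 92 × 0.30 × 0.50 × 0.70 = 9.7 CRs (10.5 points).

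A second assumed set takes 5–20% of non-CR patients transplanted and 50–90% of those then in CR. At the null it gives 92 × 0.765 × 0.05 × 0.50 = 1.8 to 92 × 0.765 × 0.20 × 0.90 = 12.7 CRs. The width of these ranges shows how little the document settles.

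**The case against.** The strongest reply is that the protocol already has a stop rule. Section 10 says response is assessed as described in Section 7.9, and Section 7.9 ends assessments at new anti-cancer therapy. If conditioning and transplant are such therapy, a post-transplant CR is never scored. The exception is also worded for progression: in Section 6.4 the object changes from response to progression and standard-of-care marrow results. Table 7-5 schedules no blood count in long-term follow-up, although an MDS CR needs hemoglobin, platelet, neutrophil and blood-blast values (Table 14-4). Sections 7.9 and Appendix B let laboratory results within 2 weeks support a CR, but only around a protocol-specified marrow, which a standard-of-care marrow may not be. Finally, such a cut-off often sits in the SAP, which is not at hand.

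Much of this stands, and it rules out three stronger readings that a reader might infer.
- *That post-transplant CRs are in fact credited to the drugs.* No section says that such a marrow is to be scored as CR. The protocol permits it but does not order it.
- *That this is the only formally tested endpoint.* The R/R MDS monotherapy cohort also has a null, an alternative and a rejection rule for ORR.
- *That duration of CR is inflated.* Section 10 does not censor it at transplant, but censoring is at the last response assessment, so the inference rests on the same unresolved reading.

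The reply does not close the gap. The stop rule excludes these CRs only if transplant is new anti-cancer therapy. The protocol never says so, and the repeated separate treatment of transplant points the other way. Footnote a extends a column that includes response assessment. The protocol itself fixes the response window, so this is a conflict in its text and not merely a detail left for later.

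**Conclusion.** The concern holds in limited form. The registrational CR rate and the AML ORR have a window with no cut-off at transplant or new therapy, the AML CR rate has no window, and the follow-up sections conflict on transplanted patients. As written, a first CR after transplant can be counted in the test against 23.5%.

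The size of any bias cannot be established from the protocol. The 7.7%, 16.3% and 29.1% figures show how sensitive the test is to 2, 4 or 6 added points when the drug is at the null. They do not estimate what happens in this trial. They assume independent patients with a common CR rate, the 30-of-92 boundary, and that the added CRs are actually scored.

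**What to change.** In Section 10, state that the CR rate (AML and MDS) and the objective response rate count only responses first met before transplant, dated from the start of conditioning, or before any other new anti-cancer therapy. Patients first meeting CR later count as non-CR in the primary analysis and are listed separately. Align Sections 6.4, 7.6 and 7.9 and Table 7-5 with this, and state there whether transplant is new anti-cancer therapy for response purposes.

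Confirm that the transplant date is captured. The protocol names no item for it; the new anti-cancer therapy item in Table 7-5 and Section 7.7 is one place it could go.

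The cost is a short text change and a date comparison in programming. The 92 patients, the 23.5% null and the power are unchanged. The downside is a possibly slightly lower reported CR rate.

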# 2.2. Study Endpoints

# 2.2.1. Primary Endpoints

The primary endpoints for this study are:

[figure not shown]
- Measurement of AEs according to National Cancer Institute Common Terminology
  Criteria for Adverse Events (NCI CTCAE) Version 4.03 or customized AE severity
  grading as defined in the protocol (Appendix A)
- CR rate for patients with AML as defined by the Investigator according to
  protocol-specified criteria (Appendix B), which are based on European Leukemia Net
  (ELN) AML recommendations (Döhner 2017), CR rate for patients with MDS as
  defined by the IWG 2006 MDS response criteria (Cheson 2006)

 8-week RBC transfusion independence rate for patients with low-risk MDS as defined by the lack of RBC transfusions for at least an 8-week consecutive period at any time after starting therapy

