The R/R Cohorts consist of 2 cohorts: 1) an R/R Safety and Expansion Cohort, and 2) an R/R MDS Magrolimab Monotherapy Expansion Cohort. The R/R Safety and Expansion Cohort consists of an initial evaluation of magrolimab monotherapy in R/R MDS/AML patients, followed by an expansion cohort of magrolimab + azacitidine in R/R MDS/AML patients. As of Amendment 3, in the first stage, patients in the R/R Safety Cohort have been treated at the maintenance dose of 30 mg/kg twice weekly; going forward, these patients will be treated weekly at the maintenance dose of 30 mg/kg, as determined by the Clinical Trial Steering Committee (CTSC) based on clinical, PK, and PD data. This safety run-in will confirm the safety profile of magrolimab monotherapy at this dose level in an expanded R/R population. Approximately 30 days after enrollment is completed in the R/R Safety Cohort, the CTSC will assess the safety data to determine whether enrollment may begin in the TN/U Dose Evaluation Cohort. In addition, the CTSC will also determine whether enrollment will proceed to an initial 36-patient R/R Expansion Cohort, based on safety and efficacy data, which will be conducted with magrolimab in combination with azacitidine as per Amendment 5. Based on emerging data, the CTSC may decide to enroll additional patients beyond 36 for further safety, efficacy, or dosing information.

The R/R MDS Magrolimab Monotherapy Cohort was added in Amendment 6. Per FDA feedback, a magrolimab monotherapy cohort in R/R MDS will be evaluated to further define the activity of magrolimab to the contribution of magrolimab + azacitidine in MDS to support a potential single-arm approval of magrolimab + azacitidine in MDS. Patients will be enrolled in a Simon's 2-stage design to evaluate for potential futility. Patients who do not achieve an objective response with magrolimab monotherapy at the protocol-defined first response assessment may have azacitidine added by discretion of the Principal Investigator with Sponsor approval, according to the schedule of azacitidine outlined in the R/R cohorts.

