If an increased dose or frequency of dosing is explored, additional cohorts will use a standard 3+3 design. Based on emerging clinical data, the CTSC may expand this cohort beyond the initial 36 patients for further safety, efficacy, and/or dosing data. In addition, individual patients may be transitioned from a magrolimab Q2W to Q4W dosing regimen by the Investigator with approval from the Medical Monitor. As of Amendment 6, up to 23 R/R MDS patients may be enrolled in an additional R/R MDS Magrolimab Monotherapy cohort. Patients will be enrolled in this cohort in a Simon's 2-stage design. With a 1-sided significance level of 0.05 and 80% power, the null hypothesis that the magrolimab monotherapy ORR is 9% will be tested against the alternative of 30%. In the first stage, 11 patients will be enrolled. If there are 1 or fewer responses observed in these 11 patients, the cohort will be stopped. Otherwise, 12 additional patients will be accrued, for a total of 23. This cohort was stopped after 11 patients enrolled per CTSC decision in October 2020. The null hypothesis will be rejected if 5 or more responses are observed in 23 patients. R/R MDS patients who do not achieve an objective response after the first protocol response assessment may have azacitidine added to magrolimab for subsequent cycles. For patients who respond to magrolimab monotherapy and then progress, azacitidine may be added to magrolimab and patients can still be continued to be treated with the combination.

The Schedule of Assessments tables for the R/R Expansion Cohort and the R/R MDS Magrolimab Monotherapy Cohort are provided in Section 7.1. The Schedule of Assessments table for the R/R Safety Cohort, which is now closed, is provided in Appendix F.

Table 3-1. Dose and Schedule for R/R AML/MDS Cohorts

		Dose Schedule (Day per 28-day Cycle)		
Cohort	Drug/Dose/Route	Cycle 1	Cycle 2	Cycle 3+
R/R AML/MDS	Magrolimab - 1 mg/kg IV	Day 1, 4	_	_
(Safety Cohort)	Magrolimab - 15 mg/kg IV	Day 8		
	Magrolimab - 30 mg/kg IV	Day 11, 15, 22	Day 1, 8, 15, 22	Day 1, 8, 15, 22
R/R AML/MDS	Magrolimab - 1 mg/kg IV	Day 1, 4	_	_
(Expansion Cohort) a	Magrolimab - 15 mg/kg IV	Day 8	_	_
	Magrolimab - 30 mg/kg IV	Day 11, 15, 22	Day 1, 8, 15, 22	Day 1 and 15
	Azacitidine - 75 mg/m² SC or IV b	Day 1-7	Day 1-7	Day 1-7
R/R MDS (Magrolimab Monotherapy Cohort) a,c	Magrolimab - 1 mg/kg IV	Day 1, 4	_	_
	Magrolimab - 15 mg/kg IV	Day 8	_	_

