	Azacitidine - 75 mg/m² SC or IV a,b	Days 1-5	Days 1-5	Days 1-5
Dose De-escalation (Magrolimab 45 mg/kg) c	Magrolimab - 1 mg/kg IV	Day 1		_
	Magrolimab - 30 mg/kg IV	Day 8, 15, 22	_	_
	Magrolimab - 45 mg/kg IV c	_	Day 1	Day 1
	Azacitidine - 75 mg/m² SC or IVª	_	_	Days 1-5

Abbreviations: CTSC = clinical trial steering committee; IV = intravenous; MDS = myelodysplastic syndrome; MTD = maximum tolerated dose; Q2W = every 2 weeks; Q4W = every 4 weeks; SC = subcutaneous.

- a. The first 6 patients will be treated with magrolimab monotherapy. If no response is observed after Cycle 2, then azacitidine can be added starting Cycle 3 and beyond.
- b. Based on data from the safety run-in, the CTSC will decide whether the expansion cohort will receive magrolimab monotherapy or magrolimab+azacitidine.
- c. If the MTD is exceeded for the safety run-in 60 mg/kg cohort, then a dose de-escalation to a magrolimab 45 mg/kg Q4W dosing regimen or alternative magrolimab dose regimen lower than 60 mg/kg (i.e., 30 mg/kg Q2W) can be explored per CTSC decision.
- d. The magrolimab expansion dosing may be 60 mg/kg, 45 mg/kg, or 30 mg/kg Q4W or Q2W based on the safety run-in CTSC decision.

A 5-day azacitidine dosing regimen will be utilized specifically for this low-risk MDS cohort to maximize efficacy and patient convenience while minimizing toxicities in this patient population. The selection of this 5-day dosing regimen is based on a randomized trial demonstrating similar hematologic responses and RBC transfusion independence and lower AE rates for the 5-day regimen compared to a 7-day regimen (Lyons 2009). It should be noted that treatment with azacitidine as monotherapy is recommended for a minimum of 6 cycles. All patients without evidence of treatment

failure, relapse after CR/CRi, or unacceptable toxicity should continue study treatment for at least 6 cycles. Reduction of azacitidine dose frequency to a Day 1 to 3 administration per month may be considered for individual patients based on safety/efficacy or individual patient circumstances with approval by the Medical Monitor or with CTSC approval for this change for all patients. Patients may be discontinued from the treatment per Investigator's discretion prior to reaching the recommended minimum cycles for any of these reasons detailed in Section 8.1.

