### Objective Response Rate (ORR) and Duration of Response (DOR)

Analysis of ORR and DOR will be conducted in the R/R MDS Magrolimab Monotherapy Cohort.

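### In the R/R MDS monotherapy cohort, responses first reached after azacitidine is added are not excluded from the CR rate or from the planned ORR and DOR analysis

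*Protocol*

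**What the plan says.** **Purpose.** Protocol Section 3.1 says that, on FDA feedback, "a magrolimab monotherapy cohort in R/R MDS will be evaluated to further define the activity of magrolimab" within the combination, in support of a possible single-arm approval. Sections 3.2 and 11.4 set a Simon two-stage design with the hypothesis worded for monotherapy ORR: 9% against 30%.

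**Added treatment.** Section 3.2 provides that R/R MDS patients "who do not achieve an objective response after the first protocol response assessment may have azacitidine added to magrolimab" for later cycles. Patients who respond to monotherapy and then progress may also add it.

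**What is counted.** Section 10 defines the MDS CR rate: "The CR rate is the proportion of MDS patients who reach morphologic CR while on study per IWG 2006 criteria". Section 11.8.1.2 adds: "Analysis of ORR and DOR will be conducted in the R/R MDS Magrolimab Monotherapy Cohort". Section 10 defines ORR for AML only. Its MDS DOR runs from the date on which objective-response criteria are first met.

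**Who is counted.** Sections 11, 11.2 and 11.8.1.1 include every patient with at least one magrolimab dose.

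**Low-risk MDS.** The primary endpoint in Section 2.2.1 is defined "by the lack of RBC transfusions for at least an 8-week consecutive period at any time after starting therapy". The first 6 patients start on magrolimab alone. Table 3-3, footnote a, says: "If no response is observed after Cycle 2, then azacitidine can be added starting Cycle 3 and beyond".

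**The concern.** The cohort's value lies in separating magrolimab from azacitidine. Non-responders, who make up most of the cohort if the 9% null is near the truth, are the patients who may cross to the combination. They remain in the denominator, and the response window stays open. Nothing in the protocol closes the window, or fixes their status as non-response, at the first azacitidine dose.

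A CR or objective response first seen on the combination can therefore enter a rate labelled monotherapy. The error runs one way, towards a better monotherapy result, and it falls on the evidence meant to show each component's contribution. DOR is affected too, because a response that begins on the combination would contribute a duration.

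**Working it through.** **1. Is there a cut-off anywhere?**

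| Element | Protocol location | Limited to the time before azacitidine? |
|---|---|---|
| MDS CR rate | Section 10 | No; open while on study |
| MDS DOR onset | Section 10 | No; first date criteria are met |
| ORR/DOR in this cohort | Section 11.8.1.2 | No |
| Analysis population | Sections 11, 11.2, 11.8.1.1 | No; all magrolimab-dosed patients |
| Hypothesis | Sections 3.2, 11.4 | Names monotherapy ORR, but no MDS ORR definition carries that out |
| Summaries split by treatment where appropriate | Section 11 | Does not say where a response after add-on belongs |

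**2. The plan's own design, reproduced.** Inputs from Section 11.4: stop if 1 or fewer of 11 respond; reject if 5 or more of 23 respond.

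P(reject | p) = Σ over x = 2 to 11 of P(X₁ = x | 11, p) × P(X₂ ≥ 5 − x | 12, p)

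- p = 0.09: 0.0425, with a 0.740 chance of stopping at stage 1.
- p = 0.30: 0.812.

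Both match the stated one-sided 0.05 and 80%, provided that p is a monotherapy response rate.

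**3. Effect on the estimate that will be reported.** With 11 patients, one combination response adds 1/11 = 9.1 points, two add 18.2 and three add 27.3. The null and alternative are 30 − 9 = 21 points apart, so two such responses cover most of that distance and three exceed it.

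**4. Illustration under assumptions.** The protocol gives no response rate for R/R MDS patients after azacitidine is added. Let q be that rate, assumed 5% to 30%, and f the share of non-responders who add it, assumed one half or all. The nearest figure in the protocol is an ORR of 17% for azacitidine in R/R AML (Section 11.4). With a true monotherapy rate of 9%, the counted rate is 0.09 + 0.91 × f × q.

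| f | q | Counted rate | P(at least 2 of 11) | P(reject) if 23 had been enrolled |
|---|---|---|---|---|
| – | 0 | 9.0% | 0.26 | 0.04 |
| 0.5 | 5% | 11.3% | 0.36 | 0.09 |
| 0.5 | 17% | 16.7% | 0.57 | 0.30 |
| 0.5 | 30% | 22.7% | 0.75 | 0.56 |
| 1 | 5% | 13.6% | 0.45 | 0.17 |
| 1 | 17% | 24.5% | 0.79 | 0.64 |
| 1 | 30% | 36.3% | 0.95 | 0.92 |

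The expected excess in the reported rate is 0.91 × f × q. It runs from 2.3 points (f = 0.5, q = 5%) to 27.3 points (f = 1, q = 30%). At q = 17% it is 7.7 points with half switched and 15.5 with all switched.

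**5. Low-risk run-in timing.** Cycles last 28 days, so Cycle 3 Day 1 is Day 57, and Days 1–56 are the only complete 8-week window before it. A patient transfused during those days who adds azacitidine on Day 57 has no qualifying window free of azacitidine. Such transfusions are likely: patients enter transfusion-dependent, and Table 7-3 requires transfusion if hemoglobin is below 9 g/dL before the Day 1 or Day 8 dose.

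**The case against.** The case on the other side has real force.

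- **The hypothesis already names monotherapy.** The open window quoted above belongs to CR, while the Simon test concerns ORR. On ordinary reading, a response first reached on two drugs is not a monotherapy response. This stands as evidence of intent, but no MDS ORR definition puts that intent into effect, and CR is plainly open.
- **Non-responders are assessed before they switch, and the SAP can set the rule.** Both are true, and the first makes the fix easy. But the protocol itself fixes the windows as open, so a SAP rule would have to narrow them.
- **The test is moot.** A reader might infer from the table that the trial faces a false-positive risk of 64%. The protocol does not support that. It records that the cohort was stopped after 11 patients by steering-committee decision in October 2020, so the 23-patient test will not be run. The 17% comes from AML; this cohort includes patients whose MDS was refractory to, or relapsed after, a hypomethylating agent. Adding azacitidine was optional and needed Sponsor approval.
- **The low-risk limb is weaker.** Its objective covers magrolimab alone or with azacitidine, it has no hypothesis test, and only the 6 run-in patients are certain to start on monotherapy. A reader might infer that the transfusion-independence endpoint is wrong. It is not; it suits that objective. Only a rate presented as monotherapy would mislead.

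**Conclusion.** The point holds for the R/R MDS Magrolimab Monotherapy Cohort. Applied as written, the CR rate and the planned ORR and DOR analysis can include responses first reached on the combination, contrary to the cohort's purpose and to its hypothesis wording. The firm size is about 9 percentage points per such response among 11 patients. The expected excess of 2 to 27 points, and all rejection probabilities, are illustrations that rest on assumed add-on response and switching rates.

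A reader might go further and say that the protocol expressly credits combination responses to magrolimab alone. It does not; the crediting follows from open windows with no cut-off. Nor does the protocol say how many patients added azacitidine or responded afterwards. The 92-patient MDS Registrational Cohort receives azacitidine from Cycle 1 and is unaffected.

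**What to change.** In Sections 10 and 11.8, for the R/R MDS Magrolimab Monotherapy Cohort:

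- Count ORR, CR and DOR onset as monotherapy responses only if documented before the first azacitidine dose.
- Class patients who start azacitidine without a prior response as monotherapy non-responders, kept in the denominator.
- Report later responses separately, as combination responses.

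For low-risk MDS patients who start on monotherapy (at least the 6 run-in patients), keep the overall transfusion-independence rate as defined. Base any monotherapy rate only on transfusion-free windows completed before azacitidine.

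This changes analysis wording and no treatment rule. It needs only the azacitidine start dates and the response and transfusion dates. The cost is that the monotherapy rates may be lower. In the low-risk run-in, the timing shown above leaves little room for a qualifying window in patients who switch at Cycle 3, and the report should say so.
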